Précis:	A randomized clinical trial that will compare two operations used for grade II - IV hemorrhoids. Patients referred to the department of surgery in Holbæk Hospital for hemorrhoids and eligible for operation will be included consecutively. Evaluation will be done by assessing symptoms, quality of life, anal continence and hemorrhoidal anatomy pre- and postoperatively.
Objectives:	Primary: Symptoms related to hemorrhoids one year postoperatively, according to a hemorrhoidal disease symptom score (HDSS) Secondary: 1) Patient satisfaction with the operation. 2) Health related Quality of Life 3) Anal continence as evaluated by two scores for symptoms of incontinence. All one year postoperatively
Population:	Male or female, ASA I-II, aged 18 to 85 at the time of randomization, referred to surgical assessment and presenting with grade II hemorrhoids refractory to banding or sclerosing and grade III og IV hemorrhoids at the surgical department, Holbæk Hospital.
Site:	Single center study. Holbæk Hospital, Surgical Department
Description of Intervention:	Hemorrhoidectomy with either Open Hemorrhoidectomy or LigaSure™ Hemorrhoidectomy
Study Duration:	48 months (from when the study opens to enrollment until completion of follow up.)
Subject Participation Duration:	One year
Estimated Time to Complete Enrollment:	36 months

Schematic of Study Design:

INTRODUCTION

Background

Hemorrhoids is one of the oldest known medical conditions. Description of hemorrhoids is found as early as 2250BC in the code of king Hammurabi in Babylon. Even though first recorded treatment is thought to be found in the "Edwin Smith Papyrus" from 1700BC¹ as of today the treatment of this benign state is still debated. A wide range of prevalence rates of hemorrhoids have been stated in part because of the varying definition, but the general consensus is that hemorrhoidal disease is a common anorectal disease affecting the quality of life of millions of people worldwide^{2 3}. Operation for hemorrhoid is one of the most common operations for benign disease in Denmark.

Hemorrhoids arise from the normal vascular structures in the anal canal also referred to as anal cushions or sinusoids as they do not contain muscular cells like arteries or veins. These cushions are typically arranged in three main columns or piles in the anal canal forming an important part of the intricate mechanism of the anal canal preventing incontinence⁴.

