Anal continence. OH and LH are both excisional operations. Anal continence has been a concern after these operations. Anal incontinence is defined as involuntary loss of air, liquid or solid stool that is a social or hygienic problem¹⁸. The anal cushions contribute to the closure of the anal canal and provide 15- 20% of maximal resting pressure of the anal canal¹⁹. A Cochrane review found that anal incontinence was reported in 1.6% of the patients after conventional hemorrhoidectomy²⁰. Another Cochrane review reported 3,6 % anal continence or hygiene problems at 1-2 years follow-up after conventional hemorrhoidectomy¹². When patients are actually asked for symptoms of incontinence a retrospective multicenter study found that 33% of the patients reported anal incontinence after hemorrhoidectomy and 10% meant this was caused by the operation²¹. Another study found some deterioration of anal incontinence after hemorrhoidectomy in patients with preoperative impaired continence²². Anal continence after LigaSure™ hemorrhoidectomy is scarcely investigated.

Previous studies comparing Open Hemorrhoidectomy and LigaSure™ Hemorrhoidectomy

Open Hemorrhoidectomy and LigaSure™ are both techniques where the hemorrhoids are excised, (ablative techniques). A few studies indicates that ablative techniques have better long term results in terms of reduction of symptoms^{11,23}.

There are so far 18 controlled studies comparing OH to LH²⁴⁻⁴¹, all designed for and using postoperative pain as major outcome variable. There are three metanalysis the largest including 11 studies^{42,43,44}. In conclusion there seems to be less post procedural pain, somewhat faster recovery, slightly less bleeding and shorter operating time after LH.

Patient' satisfaction was evaluated in a few studies with no difference between the two operations^{29,40,41}. One small study on 30 patients investigated anal continence with no difference between the two operations³⁰.

No study has investigated hemorrhoidal symptoms with a validated instrument one year or more after the operation

Rationale

Hemorrhoidal Disease is a benign disease and should be evaluated by its effect on hemorrhoidal symptoms together with its effect on quality of life.

Hemorrhoidal symptoms should be the main outcome variable when evaluating surgery for hemorrhoidal disease. This information is largely lacking.

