The use of a validated symptom score with long term follow-up could yield important information for the choice of treatment of hemorrhoidal disease.

Postoperative complications and adverse effects

Serious complications to hemorrhoidal operations occur rarely. The most commonly early complications are urinary retention, bleeding or fever/infection. Late complications are anal fissure, anal stenosis and anal incontinence. A Cochrane review reported after open hemorrhoidectomy; postoperative bleeding 2.9%, urinary retention 5.1%, anal fissure 3.1%, anal stenosis 0,9% and anal incontinence 1.6%²⁰.

Search Methods

A PubMed database search was conducted with following PICO query:

```
((("haemorrhoids"[All Fields] OR "hemorrhoids"[MeSH Terms] OR "hemorrhoids"[All Fields]) AND (((Open[All Fields] AND ("hemorrhoidectomy"[MeSH Terms] OR "hemorrhoidectomy"[All Fields] OR "haemorrhoidectomy"[All Fields])) OR Milligan-Morgan[All Fields]) OR ("diathermy"[MeSH Terms] OR "diathermy"[All Fields]))) AND (Ligasure[All Fields] OR (Ligasure[All Fields] AND ("hemorrhoidectomy"[MeSH Terms] OR "hemorrhoidectomy"[All Fields] OR "haemorrhoidectomy"[All Fields]))) AND ("complications"[Subheading] OR "complications"[All Fields])
```

A Cochrane was done searching for h(a)emorroidectomy and h(a)emorroid.

Relevant articles were chosen and by title and abstract and by reading the reference lists further texts were identified. In addition Danish and Swedish guidelines from national medical journals were included.

OBJECTIVES

Aim

To analyze and compare the long-term effects of LigaSure™ hemorrhoidectomy (LH) and Open Hemorrhoidectomy (OH) on hemorrhoidal symptoms.

Main outcome variable

Symptoms related to hemorrhoids one year postoperatively, according to a validated hemorrhoidal symptom score (HDSS)(appendix 3).

Secondary outcome variable

- 1) Patient satisfaction with the operation one year postoperatively, evaluated on a seven grade Lichert scale.
- 2) Quality of Life as evaluated by Short health Scale (SHS), Short Form 36 (SF36) and EuroQualityofLife -5 Dimensions (EQ-5D-5L) (appendix 6).
- 3) Anal continence as evaluated by the Wexner score⁴⁵, the Revised Fecal Incontinence Scale (RFIS) ⁴⁶.

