Quality of life will be evaluated by SHS, SF-36 and EQ-5D-5L, recorded by the patient preoperatively at the randomization and one, three and five years postoperatively (appendix 7).

Evaluation of anal continence

Anal continence will be evaluated using both the Wexner score and the RFIS, registered by the patient in "protokol for symptomer" (appendix 3). Five questions with a score from 0-4 resulting in a total score of 0-20 for both operations. Evaluation will be done preoperatively at randomization, after 3 months, one-, three- and five years.

Anal function will also be analyzed with anal manometry preoperatively at randomization, after 3 months, one-, three- and five years. In addition we will investigate the amount of smooth muscle in the resected specimen from the two groups indicating the amount of injury to the internal anal sphincter.

Evaluation of hemorrhoidal anatomy

Hemorrhoidal anatomy is evaluated by the surgeon using “Protokol for anatomi”(appendix 7). Late postoperative complications are also reported in “Protokol for anatomi” at follow-up.

Hemorrhoids are graded according to the Goligher classification⁶:

Grade	Grade of prolapse
I	No prolapse, just prominent blood vessels
II	Prolapse upon bearing down or by physical exercise with spontaneous reduction
III	Prolapse upon bearing down and requires manual reduction
IV	Prolapse which cannot be manually reduced

Table 1: Goligher’s classification of internal hemorrhoids

The classification of hemorrhoids is based on physical examination by the surgeon and patient history. If prolapse is not present at physical examination the patient can be classified as having grade II or III based on the patient history. External skin flaps will also be recorded in “Protokol for anatomi” (Appendix 7).

Hemorrhoidal anatomy will be evaluated preoperatively at randomization, operatively and after 3 months, one-, three- and five years.

Security control

In order to detect adverse events and non-satisfactory results a security control of the study will be performed after operation of 10 patients in each arm. An open control of the immediate postoperative course, postoperative complications and postoperative hemorrhoidal symptoms three months after the operation will be performed.

STATISTICAL CONSIDERATIONS

Study Hypothesis

There is no difference in hemorrhoidal symptoms one year after an operation for hemorrhoids performed as LigaSure™ Hemorrhoidectomy or Open Hemorrhoidectomy.

Sample Size Considerations

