
The primary outcome variable is symptom score based on the patient questionnaire. The five questions graded from 0 to 4 results in a score from 0 to 20. Preliminary data from an ongoing study in our center comparing OH with THD and using the same questionnaire shows a symptom score after 3 months of 5 with a standard deviation (SD) of 4,2. The power calculator on www.stat.ubc.ca comparing the means for two independent samples with a two sided test has been used. We postulate that a difference of 3 points in symptom score would be clinically relevant with the standard deviation of 4,2. To demonstrate a difference in mean score of 3 points with a SD of 3.5 in both groups, an alpha error of 5% and a beta error of 20%, 31 patients in each group is needed.

As for the secondary objectives analyzing anal incontinence by the Wexner score and the Revised Fecal Incontinence Scale, both consists of five questions graded from 0 to 4 results in a score from 0 to 20. Preliminary data from the study mentioned above shows a mean of 4 and SD of 3,9 for the Wexner score and a mean of 2,3 with an SD of 3,9 for the RFIS. To demonstrate a difference in mean score of 3 points with a SD of 3.9 in both groups, an alpha error of 5% and a beta error of 20%, 27 patients in each group is needed.

Patient satisfaction is analyzed after year on a scale from 1 to 7. Preliminary data from the above-mentioned study shows a mean of 5,8 and a SD of 1,6. Assuming that a difference in 1,5 points would be clinically relevant 19 patients are needed in each group with an alpha error of 5% and a beta error of 20%.

Thus a sample size of 31 patients in each group should provide sufficient power in addressing analysis of primary and secondary endpoints. We estimate that there will be a loss of 9 patients for follow up. We will include 70 patients in the study.

ETHICS

The investigators will ensure that this study is conducted in full conformity with the principles set forth in the Declaration of Helsinki seventh edition⁵¹.

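### The primary sample-size sentence prints an SD of 3.5, which gives 22–23 per group; the stated 31 comes from the SD of 4.2 given just before it, and the closing power claim also covers quality of life, which was never calculated

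*Combined protocol and SAP*

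**What the plan says.** All the sizing is in the protocol's Sample Size Considerations. For the symptom score, pilot data from another study at the centre give an SD of 4.2. The target difference is then tied to that SD: "We postulate that a difference of 3 points in symptom score would be clinically relevant with the standard deviation of 4,2". The next sentence, which carries the calculation, has a different SD: "To demonstrate a difference in mean score of 3 points with a SD of 3.5 in both groups". With alpha 5% and beta 20% it arrives at 31 per group. The section says that the calculation is a two-sided comparison of two independent means.

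Two secondary calculations follow. The Wexner score and the RFIS share one: 3 points, SD 3.9, 27 per group. Satisfaction has the other, with an SD of 1.6: "Assuming that a difference in 1,5 points would be clinically relevant 19 patients are needed in each group". The section then concludes: "Thus a sample size of 31 patients in each group should provide sufficient power in addressing analysis of primary and secondary endpoints".

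Quality of life is also a secondary outcome. The Précis lists it between satisfaction and continence ("2) Health related Quality of Life 3) Anal continence as evaluated by two scores"), the Secondary outcome variable list under Objectives repeats it, and the section on evaluating quality of life names three instruments: "Quality of life will be evaluated by SHS, SF-36 and EQ-5D-5L, recorded by the patient preoperatively at the randomization". No section gives an SD, a relevant difference or a sample size for any of them.

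**The concern.** Two consecutive sentences give different SDs for the primary outcome, and the SD in the calculation sentence does not lead to the stated result. A reader who relies on that sentence would credit the trial with over 90% power, when the SD that yields 31 gives about 80%. The sentence is also the one most likely to be copied into a publication or checked by a referee, who would find that it does not reproduce.

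The lesser matter is the scope of the conclusion. It is worded as following from the calculations above it and refers to secondary endpoints without qualification, yet one of the three numbered secondary outcomes was not calculated. A non-significant quality-of-life result could then be read against an adequacy that the protocol asserts but has not shown.

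**Working it through.** **Inputs.** From Sample Size Considerations: two-sided alpha 0.05, power 0.80, equal groups; symptom score difference 3, SD printed as 3.5 and, twice, as 4.2; Wexner/RFIS difference 3, SD 3.9; satisfaction difference 1.5, SD 1.6.

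**Formula.** Normal approximation: n per group = 2 × (1.960 + 0.842)² × (SD/difference)² = 15.70 × (SD/difference)². The exact two-sample t-test (noncentral t) is the check.

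**Reproducing the stated figures.**

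| Endpoint | Difference / SD | Normal approximation | t-test | Stated |
|---|---|---|---|---|
| Symptom score, SD 4.2 | 3 / 4.2 | 15.70 × 1.960 = 30.8, so 31 | 31.8, so 32 | 31 |
| Symptom score, SD 3.5 | 3 / 3.5 | 15.70 × 1.361 = 21.4, so 22 | 22.4, so 23 | 31 |
| Wexner / RFIS | 3 / 3.9 | 15.70 × 1.690 = 26.5, so 27 | 27.5, so 28 | 27 |
| Satisfaction | 1.5 / 1.6 | 15.70 × 1.138 = 17.9, so 18 | 18.9, so 19 | 19 |

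The two methods differ by one patient per group, and every stated figure matches one of them except the primary line at SD 3.5. That line misses by 8 or 9 per group (31 − 23, 31 − 22), which neither rounding nor choice of method explains.

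**Can SD 3.5 be rescued?** One-sided testing at SD 3.5 gives 17 or 18 per group. Raising power to 90% gives 29 or 30. A difference of 2.5 at SD 3.5 does give 31, because 2.5/3.5 = 3/4.2 = 0.714, but the text says 3 points in both sentences. Solving backwards, n = 31 for 3 points implies SD = 3 × √(31/15.70) = 4.22 (normal approximation) or 4.15 (t-test). Both are close to 4.2.

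**Power at 31 per group.** Normal approximation: Φ(difference / (SD × √(2/31)) − 1.960), with √(2/31) = 0.254.

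- Symptom score, SD 4.2: 3/(4.2 × 0.254) = 2.81; Φ(0.85) = 80.3%; t-test 79.0%.
- Symptom score, SD 3.5: 3/(3.5 × 0.254) = 3.37; Φ(1.41) = 92.1%; t-test 91.3%.
- Wexner / RFIS, SD 3.9: 85.7%; t-test 84.6%.
- Satisfaction, SD 1.6: 95.8%; t-test 95.3%.

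**Quality of life.** No sample size can be derived, because no difference or SD is given. What can be stated is the standardized difference detectable with 80% power at 31 per group, unadjusted: 2.80 × 0.254 = 0.71 SD by normal approximation, 0.72 SD by t-test. The protocol's own targets for the other endpoints are 3/4.2 = 0.71, 3/3.9 = 0.77 and 1.5/1.6 = 0.94 SD.

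**The case against.** The strongest reply is that this is one misprinted figure with no effect on the design. The section gives 4.2 twice, the stated 31 follows from it, and neither the secondary sample sizes nor the totals of 62 and 70 depend on 3.5. That stands, and it limits the point to a correction of the text. It does not remove the point, because the printed sentence does not produce its own result.

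On the concluding sentence, one can say that it summarises only the calculations just shown, that it is hedged, and that a trial need not be powered for every secondary outcome. The Rationale supports the priority given to symptoms: "Hemorrhoidal symptoms should be the main outcome variable when evaluating surgery for hemorrhoidal disease". Most of this stands too. Leaving quality of life unsized is not a fault. What remains is that the sentence refers to secondary endpoints without restriction, and quality of life is one of them.

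Two stronger readings are tempting. A reader might infer that 31 is wrong and the trial should have 22 or 23 per group. The documents do not support this: the only SD that they tie to data is 4.2, and it yields 31. A reader might also infer that the trial is underpowered for quality of life. That cannot be shown, because the documents give no target difference and specify no quality-of-life analysis, so 31 per group may or may not be adequate.

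**Conclusion.** The primary calculation is wrong as written, and the correction is minor. At the printed SD of 3.5 the requirement is 22–23 per group; the stated 31 belongs to SD 4.2. The sample size itself is not called into question. Power for the primary comparison at 31 per group should be understood as about 79–80%, not 91–92%. As a secondary point, the claim of sufficient power is unsupported for quality of life, without being shown false.

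These results rest on the protocol's own settings (two independent means, two-sided 5%, 80% power, 31 analysed per group) and on taking its SDs at face value. The 4.2 is a 3-month pilot value, accepted here because it is the SD the protocol itself uses. The 0.72 SD figure assumes an unadjusted two-sample t-test.

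**What to change.** In the primary calculation sentence, change the SD from 3.5 to 4.2, after checking it against the sponsor's record of the calculator inputs.

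Replace the concluding sentence with one limited to what was calculated, for example:

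> With 31 patients analysed per group, power is about 79–80% for a 3-point difference in symptom score (SD 4.2), about 85% for 3 points on the Wexner score or the RFIS (SD 3.9), and about 95% for 1.5 points of satisfaction (SD 1.6). Quality of life was not used to set the sample size; in an unadjusted t-test the difference detectable with 80% power is about 0.72 SD.

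The cost is one corrected figure and two replacement sentences, with no additional patients, data or analyses. The only downside is a slightly less favourable power statement.

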We will also analyze: anal function with anal manometry, anatomical result as evaluated by the surgeon, operation time, theatre time (time consumed in the operating room), postoperative complications, postoperative pain and need of analgesics, length of postoperative hospital stay and days before return to work or possibility of return to work.

SUBJECT CRITERIA

Subject Inclusion Criteria

In order to be eligible to participate in this study, an individual must meet all of the following criteria:

- Male or female aged 18 to 85 at the time of randomization
- Grade III-IV hemorrhoids and grade II hemorrhoids refractory to previous treatment with rubber band ligation or sclerotherapy.
- Hemorrhoidal symptom score of four or more
- Colonoscopy, sigmoidoscopy or rigid rectoscopy within 3 months before inclusion.
- American Society of Anesthesiologists (ASA) score of I or II. (day-care surgery)
- Provide signed and informed consent form

Subject Exclusion Criteria

An individual who meets any of the following criteria will be excluded from participation in this study:

- Previous operation of grade III and IV hemorrhoids within the last 2 years.
- Previous operation for anal incontinence.
- Active anal fistula or anal fissure
- Incontinence for solid stool

- Active immunosuppressive therapy (increased risk of anorectal sepsis)
- Cirrhosis / portal hypertension
- Mb Crohn⁴⁷

DESIGN AND METHOD

Trial Design

This is a single center randomized clinical trial comparing two operative techniques in the treatment of hemorrhoids.

Qualification of the surgeons

The surgeon should have experience from at least ten open hemorrhoidectomies and ten LigaSure™ hemorrhoidectomies before operating independently

Operation date and type of anesthesia

Operation time, theater time, operative bleeding, grading of complexity of the operation and type of anesthesia is recorded by the surgeon after the operation in “Protokol for operation” (appendix 8)

Study Interventions – Open Hemorrhoidectomy (OH)

Patient Material and Recruitment

According to the power calculation at least 62 subjects are needed for the analysis.

Compensating for an estimated loss to follow-up of approximately 10%, 70 subjects will be included in the study. See statistical considerations in a later chapter.

Subjects for this study will be recruited consecutively from patients attending the proctologic outpatient clinic at the department of surgery at Holbæk Hospital eligible for operation.

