Inclusion procedure

Subjects recruited will receive written information about the study (appendix 1).

Subjects will be offered a new appointment with one of the surgeons participating in the study offering further information if needed. It will be possible to bring an assessor.

Subjects will be offered 14 days to consider their participation. Before inclusion in the study a declaration of acceptance will be signed by the subject (Appendix 2). A checklist, “Protokol for inklusion” (appendix 5), will be used at the first visit in the surgical outpatient clinic to ensure correct inclusion and patient history will be obtained in “Protokol for anamnese” (appendix 4).

Randomization

Subjects fulfilling the inclusion criteria and accepting to participate in this study will be randomized to LH or OH. Randomization is stratified by gender. List for randomization will be obtained from www.random.org. Notes assigning the subject to either operation according to the randomization lists will be placed in sealed envelopes. Each envelope is assigned gender and number in the study (Male 1,2,3.. or Female 1,2,3..).

The envelope will be opened in the operating theatre after the patient has been anesthetized. Randomization lists and the sealed envelopes will be stored in a locked safe.

Anesthesia and thromboembolic prophylaxis

After consulting with surgeon and patient the anesthesiologist will decide type of anesthesia to use (general, spinal or epidural). Respecting any contraindications, patients will receive a preoperative perianal block with a total of 40ml of Ropivacaine 4,75mg/ml according to the technique described by Nyström et al⁴⁸.

All patients will receive thromboembolic prophylaxis with low molecular heparin unless contraindicated.

STUDY INTERVENTION The operation methods

Operations will be done in the outpatient day surgery setting in the surgical department of Holbæk Hospital. Irrational details will be recorded in "Protocol for operation" (Appendix 8). In the following description of the two operative techniques differences in operation is marked in *italics*.

STUDY INTERVENTION Open Hemorrhoidectomy

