The procedure is repeated for each hemorrhoid taking care of leaving adequate "skin bridges" between each excision.

Postoperative Care

All patients will be discharged on the day of the operation unless there are any immediate postoperative complications or if the patient is living alone without attendance at home the first 24 postoperative hours.

Standard postoperative pain treatment is initiated for all patients regardless of operation type and consists of:

Paracetamol tablet 1-gram x4/day for 7 days, hereafter p.n.

Ibuprofen tablet 400mg x3/day for the first 7 days, hereafter p.n. (patients \geq 65 years old will receive supplementary Pantoprazole tablet 40mgx1/day when using ibuprofen)

Morphine tablet 10mg p.n. Max 6 tablets/day for 3 days

Magnesia tablet 1gx2/day for 7 days, hereafter p.n.

Xylocaine gel p.n.

At discharge from the hospital and in the preoperative material (appendix 1) patients are informed that there are no limitations concerning physical activity and they are encouraged to return to daily activity as soon they feel fit enough and the postoperative pain permits it. Patients are told not to drive, operate heavy machinery or performing other potentially dangerous tasks while on morphine.

Postoperative pain and return to daily activities

During the first 14 postoperative days the patient will report postoperative pain, use of analgesics and return to daily activities or work in "Patientdagbog" (appendix 10). Since weekends and holidays can influence when a patient returns to work, patients will answer a question when they feel fit enough to return to work. *It will also be noted if the patient is self-employed.*

Immediate postoperative course

Immediate postoperative complications, postoperative pain, use of analgesics and length of hospital stay will be noted in "Sygehusprotokol" (appendix 9).

Evaluation of symptoms

The questionnaire "Protokol for symptomer" (appendix 3) is used for evaluating hemorrhoidal symptoms recorded by the subject. Five questions on pain, itching, bleeding, soiling and prolapse graded from 0-4. Resulting in a score of 0-20.

The hemorrhoidal symptoms will be evaluated preoperatively at randomization, after 3 months, one-, three- and five years.

Patient's satisfaction with the operation will be evaluated on a 7-grade Lichert scale.

Evaluation quality of life

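### The stated minimum of 62 evaluable patients, the enrolment of 70 and the expected loss of 9 do not agree: 70 less 9 is 61

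*Combined protocol and SAP*

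**What the plan says.** The plan sizes the trial in two places.

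- Design and Method, Patient Material and Recruitment: "According to the power calculation at least 62 subjects are needed for the analysis". It continues: "Compensating for an estimated loss to follow-up of approximately 10%, 70 subjects will be included in the study".
- Statistical Considerations, Sample Size Considerations: the primary calculation leads to 31 per group, and the section concludes "Thus a sample size of 31 patients in each group should provide sufficient power in addressing analysis of primary and secondary endpoints". It then says "We estimate that there will be a loss of 9 patients for follow up" and gives the same enrolment of 70.

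The primary endpoint is the symptom score at one year. The loss sentence does not say by which visit the 9 patients are lost. Two parts of the document bear on this and point in different directions:

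- The Précis gives one year of participation per subject, 36 months of enrolment and a study duration of "48 months (from when the study opens to enrollment until completion of follow up".
- Evaluation of symptoms has a longer schedule: "The hemorrhoidal symptoms will be evaluated preoperatively at randomization, after 3 months, one-, three- and five years".

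The Sample Size section also prints two standard deviations for the primary score. It calls a 3-point difference clinically relevant with an SD of 4.2, and the next sentence reads "To demonstrate a difference in mean score of 3 points with a SD of 3.5 in both groups".

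**The concern.** Required number, allowance for loss and enrolment should satisfy one subtraction, and here they do not. The two sections share the same minimum and the same enrolment but carry different loss assumptions: about 10% in one, 9 of 70 in the other. On the second, the expected number at one year falls below the number that the plan says it needs.

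What is at stake is mainly a clear benchmark. When results are reported, observed attrition and the number analysed will be compared with the plan, and the plan offers two loss figures, one of which contradicts its own minimum. The possible cost in power is small.

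**Working it through.** **Inputs.** From Sample Size Considerations: difference 3 points, SD 4.2 (3.5 also printed), two-sided alpha 5%, power 80%, 31 per group, loss 9, enrolment 70. From Patient Material and Recruitment: minimum 62, loss about 10%, enrolment 70.

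**1. Reproduce the stated size.** Normal approximation, n per group = 2 × (1.960 + 0.842)² × SD² / difference².

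- SD 4.2: 2 × 7.849 × 17.64 / 9 = 30.8, so 31 per group and 62 in total. This is the plan's figure.
- SD 3.5: 2 × 7.849 × 12.25 / 9 = 21.4, so 22 per group.

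The stated 31 therefore rests on SD 4.2. The t-test version at SD 4.2 gives 31.76, so 32.

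**2. Check the allowance for loss.**

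| Loss assumed | Share of 70 | Patients left |
|---|---|---|
| 7 | 10.0% | 63 |
| 8 | 11.4% | 62 |
| 9 | 12.9% | 61 |

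The loss of about 10% fits 62 and 70: 62 / 0.9 = 68.9, or per arm 31 / 0.9 = 34.4, rounded up to 35 and doubled to 70. The plan shows neither calculation, so both routes are reconstructions. A loss of 9 does not fit 62 and 70. Keeping 62 after 9 losses would need 62 + 9 = 71 enrolled, or 72 if 9/70 is treated as a rate (62 / (1 − 9/70) = 71.1).

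**3. When is the loss counted?** 48 − 36 = 12 months, which with one year of participation suggests that the 9 refers to one year. The three- and five-year visits leave open that it refers to longer follow-up. In that case no shortfall at one year follows.

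**4. Cost in power if the loss is by one year.** Normal method: power = Φ(3 / (SD × √(1/n₁ + 1/n₂)) − 1.960).

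- SD 4.2, 31 + 31: standard error 4.2 × √(2/31) = 1.067; 3 / 1.067 − 1.960 = 0.852; power 80.3%.
- SD 4.2, 30 + 31: standard error 4.2 × √(1/30 + 1/31) = 1.076; 3 / 1.076 − 1.960 = 0.829; power 79.6%.
- By t-test the same two cases give 79.0% and 78.3%.
- SD 3.5, 30 + 31: 91.7% (normal) or 90.9% (t-test).

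The difference at SD 4.2 is about 0.7 points by either method. The secondary sizes stated in the section, 27 and 19 per group, are still met at 30 + 31.

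**The case against.** The strongest reply is that this is forecast noise. Eight against nine losses is within the error of any attrition estimate, and 79.6% still rounds to 80%. The choice between normal and t-test methods moves power at 31 + 31 by 1.3 points (80.3% against 79.0%), more than the missing patient does. The loss is also undated, and the Précis figures that suggest one year themselves sit uneasily with the three- and five-year visits. All of this stands, and it keeps the point minor and the one-year shortfall conditional. It does not remove the mismatch: the section gives 31 per group, 9 and 70 as plain counts, and they do not subtract correctly. If the 9 was meant for later visits, the section says neither that nor what loss it expects at one year.

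A reader might infer that the 9 is the mistake, because about 10% fits the other two figures. The documents do not support going that far. The three numbers are only jointly inconsistent; the enrolment of 70 could equally be the one that is out.

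A reader might also infer that the trial is underpowered. That does not follow either. The gap is one patient, and at the SD of 3.5 printed in the calculation sentence there is no shortfall at all.

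**Conclusion.** The inconsistency is real and minor. A minimum of 62, an enrolment of 70 and a loss of 9 cannot all hold at the one-year endpoint: 61 would remain, and 8 is the largest loss that leaves 62. The subtraction is certain. The shortfall at one year depends on all 9 being lost by then, which is the likelier reading but is not stated.

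Its size is one patient and about 0.7 points of power, assuming a 3-point difference, SD 4.2 and near-equal arms. The SD of 3.5 against 4.2 is a separate inconsistency. It decides whether any power shortfall exists, but not whether the counts agree.

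**What to change.** Use one loss figure in Patient Material and Recruitment and in Sample Size Considerations, and tie it to the one-year visit. Two ways are open.

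- **(a)** State that 70 included allows for at most 8 losses by one year (11.4%), leaving 62 evaluable in total, if the sponsor can support that figure; nothing in the documents supports 8 over 9. The wording should say 62 in total: 31 per group follows only if arms and losses are balanced, and the Randomization section describes gender strata but no blocking. Cost: one sentence in each section.
- **(b)** Keep 9 and state 61 expected evaluable, with power at SD 4.2 and near-equal arms by one named method: 79.6% (normal) or 78.3% (t-test). The minimum of 62 in Patient Material and Recruitment, and the 31 per group and 20% beta error in Sample Size Considerations, must then be amended to match; otherwise the contradiction remains. Cost: a few more sentences and a slightly less favourable stated figure.

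Enrolling 71 would also close the gap arithmetically, but one patient does not require it. The two SDs should be reconciled at the same time, as a separate correction.
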